#### 3.3 Study Design, Methodology, and Experimental Manipulations

The study consists of a two group design. Assignment to each of the two experimental conditions is determined randomly upon the volunteers’ arrival to the study webpage. However, the website will be programmed to achieve equal sample size across the two groups. The duration of participation for each volunteer is estimated to be about 60 minutes (total, including both time-points). Volunteers will complete the following as part of the study:

- a. HBMT: Volunteers will complete a computer-based hostile bias modification training where they are instructed to complete word fragments (words with missing letters) to form non-aggressive words. The word fragments are based on similar stimuli used in prior research on hostile bias (Anderson, Carnagey, & Eubanks, 2003; DeWall & Bushman, 2009). This task was validated in a previous study (WRAIR # 2574).
- b. Angry Cognitions Scale/HAB measure: This measure asks respondents to read hypothetical scenarios and indicate how they would interpret and respond to them. It was developed by Martin and Dahlen (2007) and will be used as a measure of HAB.
- c. Trait anger Scale: Brief measure of trait anger validated by Wilk et al., (2015).
- d. State Aggression Survey: This survey is adapted from several others in the literature to measure variance along the normal spectrum of aggressive behaviors in daily life that the average person might display (Álvarez-García, et al., 2016; Deffenbacher, et al., 2001; Deffenbacher, J. et al., 2002). The survey specifically asks about driving behaviors (e.g., yelling at other drivers), and public online behaviors (e.g., posting mean comments on social media), as well as generic public displays of aggression items (e.g., Gotten angry and slammed a door).

- e. State Emotion Survey: A short measure of state (current or recent) emotions over the preceding 24 hour period adapted from Goldberg et al., (2006) and Quartana and Burns (2007).
- f. Demographic questions: Volunteers will be asked to provide their age (whole number, not birth date), highest level of education, and gender. These will be used as statistical controls in analyses.

Volunteer recruitment and data collection will be done online by ARL AI's and/or staff with assistance from volunteerscience.com (the online experimental platform). Volunteers will be recruited via Amazon Mechanical Turk (MTurk) to the experimental webpage and complete informed consent electronically. A description of this clinical trial will be available on <http://www.clinicaltrials.gov>. Additionally a copy of the informed consent may be posted to a public website no later than 60 days after enrollment is completed.

Time-point 1: Volunteers will be randomly assigned to complete either the real or fake HBMT. Volunteers will also complete a brief vignette reading HAB activity, a brief measure of trait (what is typical for them) aggression, and state (how they have felt recently) anger.

Time-point 2: Volunteers will be asked to return no sooner than 24 hours and no later than 96 hours from when they completed time-point 1 to complete a following up HAB assessment (second vignette interpretation task) and brief surveys asking about aggressive behaviors and state anger during the preceding 24 hour period.

Mechanism for inviting volunteers back to complete time-point 2: The two-time point nature of this study will be explained to volunteers in both the study advertisement and in the ICD.

Additionally, a feature on MTurk will allow the volunteerscience.com to send a daily e-mail to time-one volunteers inviting them back to time-point two. This can be done without MTurk revealing the e-mail addresses of the volunteers. The e-mail will remind volunteers to please return at any point between 24 hours and 96 hours from when they completed the first time-point.

Upon completion of each time-point, the webpage will thank volunteers for their participation. Volunteers will be paid part of the payment at the end of time-point one and the remaining payment after completing time-point two (see section 10.6).

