## **4 STUDY OBJECTIVES**

### **4.1 Primary Objectives**

- a. To determine the efficacy of HBMT in reducing anger and aggressive behavior in daily life.
- b. To determine the longevity and depreciation of HBMT effects on real life anger and aggression over time (between 24-96 hours post HBMT).

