### **5.2 Secondary Hypothesis**

- a. The effects of HBMT on anger and aggression will diminish over time. In other words, larger effects of HBMT will be observed for volunteers returning sooner (vs later) after time-point one.
- b. We anticipate the most robust impact of HBMT on anger and aggression on high versus low stress days (per self-report).

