## 8.5 Randomization and Volunteer Assignment

Volunteer assignment to each of the two experimental conditions is semi-randomized (i.e. random except that computer ensure equal sample sizes across experimental conditions). The randomized assigning of participants is done by the study web-page/program at volunteerscience.com. The computer program randomly assigned volunteers to one of the two conditions when they begin the study.

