## 9 STATISTICAL METHODS AND DATA ANALYSIS

### 9.1 Analyses for Main Study Hypotheses

Between group differences (comparing real vs. fake HBMT) in the change in state anger and state HAB across time points (change from time-point one to time-point two) will be primarily assessed with a mixed-designs ANOVA. Between group differences in state aggression measured at time-point two will be assessed with a General Linear Models (GLM) analysis controlling for trait anger and demographics (age and gender).

We will also plot effect of group comparing real vs. fake HBMT and time between time-points (24-96 hours) on change scores (time 2 anger/aggression minus time 1 anger aggression) and analyze this using a linear regression with an interaction term.

Lower order effects will be tested using corrected Fishers LSD, Tukey, Scheffe, or other pairwise test as appropriate. Appropriate data-transformations may be used as necessary to satisfy significance test requirements. Lower order effects will also be assessed with pairwise dependent means t-tests. Age and gender will be controlled as covariates. Mediation analyses (if used) will be performed using non-parametric Monte-Carlo bootstrapping procedures using PROCESS (see Hayes, 2017).

We may use age, gender, and trait measures as control variables in analyses.

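### Return time is chosen by the volunteer after randomisation, so the group-by-delay regression can describe an association but cannot determine how long the HBMT effect lasts

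*Combined protocol and SAP*

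**What the plan says.** Allocation is settled at the start of time-point one (section 8.5): "The computer program randomly assigned volunteers to one of the two conditions when they begin the study". Nothing else is randomised. On the second visit, section 3.3 says "Volunteers will be asked to return no sooner than 24 hours and no later than 96 hours from when they completed time-point 1", and the daily reminder asks people to "please return at any point between 24 hours and 96 hours from when they completed the first time-point". No section assigns, staggers or randomises the return time, and no one is assessed more than once after the day of training.

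Section 4.1b makes it a primary objective "To determine the longevity and depreciation of HBMT effects on real life anger and aggression over time". The summary of objectives in 3.1 does not list this aim, and the matching hypothesis, 5.2a, is secondary: "larger effects of HBMT will be observed for volunteers returning sooner (vs later) after time-point one".

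The analysis is in 9.1: "We will also plot effect of group comparing real vs. fake HBMT and time between time-points (24-96 hours) on change scores", and the plan will "analyze this using a linear regression with an interaction term". The change scores are defined as time 2 minus time 1 for both anger and aggression. The same section takes age and gender as covariates and allows trait measures as optional controls. It plans no covariate-by-group term. Section 7.2 sizes the trial for a main effect of d = .4 and gives no power for the delay question.

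**The concern.** Fading is a statement about what happens to the same kind of person as time passes. Here the only evidence on it is a comparison of different people who came back at different times by their own choice, after allocation. If the people who come back early are also those who respond more (or less) to HBMT, the interaction reflects who they are and not how much time has passed. The same follows if the training itself shifts when people return.

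A significant interaction could then be selection, and real fading could be hidden by selection of the opposite sign. A non-significant result would say little, because the test is weak. In each case objective 4.1b would get an answer that the design cannot support.

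**Working it through.** **The plan's own figure.** For d = .4, SD 1, two-sided 5% and 80% power, n per arm = 2 × (1.96 + .842)² / .4² = 98.1, so 99; the exact t-test gives 100 per arm, 200 in total. This reproduces section 7.2. It concerns the arm difference averaged over delay.

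**Precision of the interaction.** Inputs: 200 completers, 100 per arm (7.1, 7.2); window 24-96 h (3.3); residual SD 1. Delays are assumed uniform, since the documents give no distribution.
- SD of delay = 72/√12 = 20.8 h, so the window spans √12 = 3.46 SD.
- Standard error of the interaction = 2/√200 = .141 per SD of delay, or .141 × 3.46 = .49 SD over the window.

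**Power for real fading.** Take a fall from .6 to .2, which averages to the planned .4.
- z = .4/.49 = .82.
- Two-sided: P(Z > 1.96 − .82) + P(Z < −1.96 − .82) ≈ 13%. One-sided: P(Z > 1.645 − .82) ≈ 20%.
- Simulation with delay independent of the person gave 14% and 21%. A fall of .8 SD (.8 to 0) had 35% two-sided.
- The fall detectable with 80% power, two-sided, is (1.96 + .842) × .49 = 1.37 SD, over three times the planned effect.

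Both versions are shown because 9.2 reserves one-tailed tests for the hypotheses in 5.1, and the fading hypothesis is in 5.2.

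**When selection biases the interaction.** All cases below have no true fading. The correlations and modifiers are assumptions.
1. *Early and late returners differ in outcome level, equally in both arms* (correlation .3, same HBMT effect for all). The difference goes into the delay main effect: bias about 0, false positives 4.7%.
2. *A trait predicts delay and modifies the response to HBMT.* Spurious change over the window ≈ r × modifier × 3.46.
   - r = .3, modifier .2: .21 SD.
   - r = .3, modifier .3: .31 SD (simulated .30).
   - r = .4, modifier .3: .42 SD (simulated .41).
   - Simulated two-sided false-positive rates run from 7% to 12% across this range.
   - With a stronger link, r = .5 and modifier .2, the change is .34 SD with 10.4% false positives.
3. *HBMT changes who returns when.* With the same HBMT effect for everyone, but a trait that predicts the outcome (.3 SD per SD) correlating .5 with delay in one arm and .9 in the other, the change is .3 × (.9 − .5) × 3.46 = .42 SD (simulated .40), with 13.4% false positives.

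Reversing the sign of a correlation or modifier reverses the bias, so a false rise or masked fading is equally possible.

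**Does the covariate wording in 9.1 help?** Entering the trait as a main effect leaves the bias in place. At r = .5, false positives were 10.4% (modifier .2) and 24.1% (modifier .4) without it, and 11.6% and 28.9% with it. When delay was drawn independently of the trait, the rates were 5.2-5.4%.

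**Outcome.** Section 8.8 gives the state emotion questionnaire at both time-points, but the state aggression measure only at time-point two. The change score in 9.1 therefore exists for anger and not for aggression.

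**The case against.** *Different kinds of people returning early and late is not in itself a source of bias.* This stands. A reader might infer that any link between return time and, say, conscientiousness or anger spoils the interaction. It does not if the link and its effect on outcome are the same in both arms (case 1).

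*The size is assumed.* This also stands. No document gives a trait-delay correlation or a modifier. A bias of .21-.41 SD is also smaller than the test's own standard error of .49 SD, so at these inputs imprecision is the larger problem and low power the firmer part of the point.

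*The plan is already partly cautious.* Hypothesis 5.2a speaks of people returning sooner or later, which is close to associational wording, and 9.1 is not limited to group, delay and their product. But main-effect covariates do not address a modifier of response, and 4.1b still claims to determine duration.

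*Nothing says that a null result will be read as durability.* Correct; a reader might suppose so, but no section states it. Nor does any section guard against it, and a null result is likely even if fading is real.

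A reader might also infer that the main result is compromised. This point does not reach it: the arm comparison averaged over delay keeps its randomisation here. Loss of up to 50% between visits is a separate matter.

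**Conclusion.** The point holds in limited form. The regression in 9.1 can describe how the arm difference varies with self-chosen return time. It cannot determine longevity or depreciation, because neither differential response by early and late returners nor an effect of HBMT on return time is excluded. Under the stated assumptions the spurious change is about .21-.41 SD over 72 h, of unknown sign, with 7-12% false positives in place of 5%. Power for a fall from .6 to .2 is about 13% two-sided or 20% one-sided, given uniform delays and 200 completers. It should be corrected because 4.1b is listed as a primary objective, but Hypothesis 1 does not depend on it. The documents do not support saying that the interaction will be biased, or that it would be biased towards fading.

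**What to change.** (a) Restate 4.1b and 5.2a as an exploratory association between self-chosen return time and the arm difference. Report that difference with 95% intervals at 24, 48, 72 and 96 h from the fitted line, and report return time by arm. State that a non-significant interaction is not evidence of persistence. With uniform delays the intervals would be about ±.32 SD at 48 and 72 h (1.96 × .141 × √(1 + .58²), where .58 = 12/20.8) and ±.55 SD at 24 and 96 h (1.96 × .141 × √(1 + 1.73²), where 1.73 = 36/20.8), which shows the reader how little the data can say at the edges.

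(b) As a sensitivity analysis, add trait anger, state anger and stress, each with its group interaction. Section 8.8 collects all three before training. The time-point-one HAB measure comes after training and should not be used this way. Say that this deals with measured modifiers only (conscientiousness and workload are not measured) and costs a little precision.

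(c) For aggression, use the time-2 score as the outcome in the delay regression.

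The cost is a change of wording and a few extra model terms, with no new data; section 11.3 requires amendments to be approved before use. I would not go further and randomise the timing of invitation e-mails. The window would stay open to everyone, so the contrast would be diluted, and delayed reminders could cost returns that the main comparison needs.

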### **3.4 Efficacy Data Collected**

Main endpoints for the study include: self-report measures of HAB and self-report measures of daily aggressive behaviors.

### **3.5 Statistical Procedures**

SPSS will be used for statistical analyses. Specific tests to be used are described in Section 9.

## **4 STUDY OBJECTIVES**

### **4.1 Primary Objectives**

- a. To determine the efficacy of HBMT in reducing anger and aggressive behavior in daily life.
- b. To determine the longevity and depreciation of HBMT effects on real life anger and aggression over time (between 24-96 hours post HBMT).

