**Appendix F**

## State Aggression Questionnaire

Please indicate how often you have done each behavior during the past **24 hours**.

During the **PAST 24 HOURS**, how often have you:

Get angry with someone and yell or shout at them.

1 = Never      2 = One Time      3 = Two Times      4 = Three or Four Times      5 = Five or more times

Get angry with someone and kick or smash something, slam the door, punch the wall, etc.

1 = Never      2 = One Time      3 = Two Times      4 = Three or Four Times      5 = Five or more times

The following set of questions is asking about your **ONLINE BEHAVIOR OVER THE PAST 24 HOURS**.

I have removed or refused another person on a contact list for a chat, social network, or instant messaging program, without him/her doing anything and only for being who he/she was

1 = Never      2 = One Time      3 = Two Times      4 = Three or Four Times      5 = Five or more times

I have posted rude or unfriendly comments about someone on social networks.

1 = Never      2 = One Time      3 = Two Times      4 = Three or Four Times      5 = Five or more times

I have insulted someone using text messages or instant messaging programs (e.g., WhatsApp, SMS).

1 = Never      2 = One Time      3 = Two Times      4 = Three or Four Times      5 = Five or more times

I have made a false complaint about someone on a forum, social network, or online game.

1 = Never      2 = One Time      3 = Two Times      4 = Three or Four Times      5 = Five or more times

I have plotted with other people to ignore someone on social networks.

1 = Never      2 = One Time      3 = Two Times      4 = Three or Four Times      5 = Five or more times

I have posted or shared rumors or negative comments or negative news about someone on a social network

1 = Never      2 = One Time      3 = Two Times      4 = Three or Four Times      5 = Five or more times

\*I have “liked”, shared, or otherwise demonstrated support for negative content about another person online or on social media.

1 = Never      2 = One Time      3 = Two Times      4 = Three or Four Times      5 = Five or more times

The following questions are asking about your **DRIVING BEHAVIORS OVER THE PAST 24 HOURS**

Have you driven in the past 24 hours: Yes/No

I have called other drivers names aloud (e.g., “Jerk!”, “Idiot!”)

1 = Never      2 = One Time      3 = Two Times      4 = Three or Four Times      5 = Five or more times

I have made negative comments about other drivers

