**Appendix H**

## State Emotion Questionnaire

How well do the following statements describe how you have **FELT OVER THE PAST 24 HOURS?**

I have felt angry.

1 = Extremely uncharacteristic of me.	2	3	4	5 = Extremely characteristic of me.
---------------------------------------	---	---	---	-------------------------------------

I have felt joyful.

1 = Extremely uncharacteristic of me.	2	3	4	5 = Extremely characteristic of me.
---------------------------------------	---	---	---	-------------------------------------

I have felt stressed.

1 = Extremely uncharacteristic of me.	2	3	4	5 = Extremely characteristic of me.
---------------------------------------	---	---	---	-------------------------------------

I have been energetic.

1 = Extremely uncharacteristic of me.	2	3	4	5 = Extremely characteristic of me.
---------------------------------------	---	---	---	-------------------------------------

I have been relaxed.

1 = Extremely uncharacteristic of me.	2	3	4	5 = Extremely characteristic of me.
---------------------------------------	---	---	---	-------------------------------------

I have gotten frightened easily.

1 = Extremely uncharacteristic of me.	2	3	4	5 = Extremely characteristic of me.
---------------------------------------	---	---	---	-------------------------------------

I have gotten irritated easily.

1 = Extremely uncharacteristic of me.	2	3	4	5 = Extremely characteristic of me.
---------------------------------------	---	---	---	-------------------------------------

I have not been easily annoyed.

1 = Extremely  
uncharacteristic  
of me.

2

3

4

5 = Extremely  
characteristic of  
me.

Citation: Goldberg, L. R. (1999). A broad-bandwidth, public domain, personality inventory measuring the lower-level facets of several five-factor models. In I. Mervielde, I. Deary, F. De Fruyt, & F. Ostendorf (Eds.), *Personality Psychology in Europe*, Vol. 7 (pp. 7-28). Tilburg, The Netherlands: Tilburg University Press.

Goldberg, L. R., Johnson, J. A., Eber, H. W., Hogan, R., Ashton, M. C., Cloninger, C. R., & Gough, H. C. (2006). The International Personality Item Pool and the future of public-domain personality measures. *Journal of Research in Personality*, 40, 84-96.

Quartana, P. J., & Burns, J. W. (2007). Painful consequences of anger suppression. *Emotion*, 7(2), 400-414.

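### Time-2 anger and aggression look back 24 h, so the longevity analysis covers 0-96 h after HBMT rather than the 24-96 h stated in objective 4.1b

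*Combined protocol and SAP*

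**What the plan says.** Section 4.1 makes longevity a primary objective (item b): "To determine the longevity and depreciation of HBMT effects on real life anger and aggression over time (between 24-96 hours post HBMT". Section 3.3 asks volunteers to come back "no sooner than 24 hours and no later than 96 hours from when they completed time-point 1" and then to complete "brief surveys asking about aggressive behaviors and state anger during the preceding 24 hour period".

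Both instruments carry that look-back. The aggression form (Appendix F) begins "Please indicate how often you have done each behavior during the past" and gives 24 hours as the period. The emotion form (Appendix H), which supplies state anger, asks how the respondent has "FELT OVER THE PAST 24 HOURS".

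Section 9.1 describes the longevity analysis: "We will also plot effect of group comparing real vs. fake HBMT and time between time-points (24-96 hours) on change scores". It will then "analyze this using a linear regression with an interaction term". The time variable is thus the moment of return. Section 7.2 uses the same 24-96 h range for the delay between training and behavioural assessment. No section adjusts for the look-back or says which hours after training the outcomes describe. Hypothesis 5.2a predicts that the effect fades, so that earlier returners show more of it.

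**The concern.** The interval between sessions says when the form was filled in. The behaviour and anger being reported occurred up to 24 h earlier. Someone who returns at 24 h describes the first day after training and nothing later, yet the plan places that report at the start of a 24-96 h axis.

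What is at stake is the time range attached to a primary-objective conclusion. HBMT is described as partly a priming procedure, so an effect confined to the first hours is a plausible rival to lasting change. Under the plan as written, such an effect could be read as one that persists into, and then declines within, 24-96 h.

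**Working it through.** **Inputs from the documents.** Return time t is 24 to 96 h (section 3.3). Recall is 24 h (section 3.3, Appendices F and H). The time variable is the interval between sessions, and the test is a group-by-time interaction in a linear regression (section 9.1).

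**Assumptions, not in the documents.** The shape and speed of decay, and, for illustration only, return times spread evenly over 24-96 h. Recall is treated as a simple average over the window. This is an approximation, because aggression is a banded frequency and anger a summary rating.

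**1. The plan's own range.** 24-96 h is correct for return times. The hours reported on are t-24 to t:

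| Return t | Hours described | Midpoint |
|---|---|---|
| 24 h | 0-24 | 12 h |
| 48 h | 24-48 | 36 h |
| 96 h | 72-96 | 84 h |

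Together the windows cover 0-96 h, with midpoints from 12 to 84 h. A window includes part of the first 24 h whenever t < 48 h. With evenly spread returns that is (48-24)/(96-24) = 1/3 of volunteers. On average half of each such window lies in the first 24 h, so 1/3 x 1/2 = 1/6 of all recalled time does.

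**2. Exponential decay.** Let the effect at hour s be e^(-ks), with k = ln 2 / half-life.

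- Recalled effect divided by the effect at t: (e^(24k) - 1)/(24k).
- Recalled effect divided by the effect at t-12: sinh(12k)/(12k).
- Equivalent time shift: ln(first ratio)/k.

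| Assumed half-life | Ratio, dated at t | Ratio, dated at t-12 | Shift |
|---|---|---|---|
| 48 h | 1.20 | 1.01 | 12.3 h |
| 24 h | 1.44 | 1.02 | 12.7 h |
| 12 h | 2.16 | 1.08 | 13.4 h |
| 6 h | 5.41 | 1.35 | 14.6 h |

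For example, with a 24 h half-life the effect at 24 h is 0.50 of its starting size, while the recalled value is 1.44 x 0.50 = 0.72.

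**3. Linear decay to zero at 96 h.** The effect at s is 1 - s/96, and its mean over t-24 to t is 1 - (t-12)/96. Dated at t, the fitted line reaches zero at 96 + 12 = 108 h. Dated at t-12, it reaches zero at 96 h. The slope is the same either way, -1/96 = -0.0104 per hour.

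**4. An effect that stops.** An effect ending at hour T can still appear in reports made up to T+24 h, which is the largest possible misdating. If it is constant for 12 h and then zero, the recalled effect at return t is (36-t)/24 for t from 24 to 36 h. It is half-size at 24 h and nil from 36 h. The true effect is zero throughout 24-96 h, yet the expected group-by-time slope is not.

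**5. What does not change.** Subtracting 12 h from every t leaves the interaction coefficient as it was; only the group term at the new origin moves. In one simulated data set of 200, the interaction had t = 0.906 and p = 0.366 with shifts of 0, 12 and 24 h. The sample size does not involve the time axis: d = 0.4, two-sided alpha 0.05 and 80% power give 99.1 per arm, consistent with the plan's 100 per arm and 200 in all.

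**The case against.** The strongest reply is that no planned test changes. Hypothesis 5.2a is worded by how soon volunteers return, and section 9.1 names its variable accurately. The slope and p-value survive any constant shift, and the Hypothesis 1 comparison and sample size are untouched. Section 9.1 promises a plot and an interaction test, with no estimate at a named hour. The recall period is openly stated in the summary and on both forms. The half-lives are assumed, and the 6 h figure is a ratio to an effect already down to about 6% of its starting size at 24 h. The midpoint itself presumes even exposure and recall across the window.

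Most of this stands, and it limits the point to the dating and level of the effect. It does not dispose of it. Objective 4.1b asks about a specific interval after training. The disclosed recall period is never carried into that objective or into the analysis, and a valid p-value for a slope does not say in which hours the fading took place.

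A reader might also infer that HAB needs its own time axis, since the Angry Cognitions Scale is answered as of the session. The longevity regression in section 9.1 covers anger and aggression only, so there is no planned HAB analysis to correct here. Separately, section 8.8 lists the aggression form at time-point two only, so its planned change score cannot be computed as written. That is a different defect; the dating applies to whichever aggression outcome is analysed.

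**Conclusion.** The point holds in limited form. The stated 24-96 h is the range of return times; the outcomes describe 0-96 h. If the effect decays, plotting it at return makes it too high for the hour shown, or last too long, by about 12 h (12.3 to 14.6 h for assumed half-lives of 48 to 6 h) and at most 24 h.

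Two stronger readings are tempting, and the documents support neither. The first is that persistence is overstated outright. That requires decay, which the plan hypothesises but has not shown. Even then the decay rate is not distorted: the exponential half-life is preserved, and so is the linear slope when the effect lasts through 96 h. The second is that the trial has no information on 24-96 h. Every return at 48 h or later lies wholly inside that range.

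The change is worth making because it corrects the time range of a primary-objective conclusion at almost no cost.

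**What to change.** - **Section 4.1b:** state that the objective covers behaviour and anger 0-96 h after HBMT, with 24-96 h being the return time.
- **Section 9.1:** state that a return at t reports on t-24 to t. Plot and interpret anger and aggression effects at the window midpoint, t-12, on an axis of 12-84 h, and say that the midpoint is an approximation.
- **Claims beyond 24 h:** base them on the group difference among volunteers returning at 48 h or later. A line fitted to all returns borrows from reports that include the first 24 h, so its value at 48 h does not serve.

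**Cost.** Wording, a relabelled axis and one subset comparison; no new items or volunteers. The subset estimate is less precise. If returns were evenly spread, about 2/3 x 200 = 133 completers would remain, and the standard error would be about sqrt(200/133) = 1.22 times that of the full sample. Return time is chosen by the volunteer, so the subset comparison shares that limitation with the planned regression. The longevity claim is likely to become slightly less favourable.
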